10.2 Data collection

Designated investigator staff will enter the data required by the protocol into the Electronic Case Report Forms using fully validated software that conforms to 21 CFR Part 11 requirements. Designated investigator site staff will not be given access to the EDC system until they have been trained. Automatic validation programs check for data discrepancies and, by generating appropriate error messages, allow the data to be confirmed or corrected before transfer of the data to the CRO working on behalf of Novartis. The Investigator must certify that the data entered into the Electronic Case Report Forms are complete and accurate. After database lock, the investigator will receive a CD-ROM or paper copies of the subject data for archiving at the investigational site.

Data not requiring a separate written record will be defined in the Site Operations Manual and [Assessment schedule](#) and can be recorded directly on the CRFs. All other data captured for this study will have an external originating source (either written or electronic) with the CRF not being considered as source.

All data should be recorded, handled and stored in a way that allows its accurate reporting, interpretation and verification.

CRO staff working on behalf of Novartis review the data entered into the eCRFs by investigational staff for completeness and accuracy and instruct the site personnel to make any required corrections or additions. Queries are sent to the investigational site using an electronic data query. Designated investigator site staff is required to respond to the query and confirm or correct the data. If the electronic query system is not used, a paper Data Query Form will be faxed to the site. Site personnel will complete and sign the faxed copy and fax it back to the CRO working on behalf of Novartis who will make the correction to the database.

Concomitant medications entered into the database will be coded using the WHO Drug Reference List, which employs the Anatomical Therapeutic Chemical classification system. Medical history/current medical conditions and adverse events will be coded using the Medical dictionary for regulatory activities (MedDRA) terminology.

Laboratory samples will be processed centrally and the results will be sent electronically to Novartis (or a designated CRO).

Commercially Confidential Information

10.3 Data Monitoring Committee

Not required.

10.4 Adjudication Committee

Not required.

11 Data analysis

11.1 Analysis sets

For all analysis sets, subjects will be analyzed according to the study treatment(s) received. The study has four parts, and the safety and efficacy analysis will be presented for period 1, period 2 and period 3 combined, and separately for period 4.

The safety analysis set will include all subjects that received any study drug.

The PK analysis set will include all subjects with available PK data and no protocol deviations with relevant impact on PK data.

Commercially Confidential Information

11.2 Subject demographics and other baseline characteristics

All data for background and demographic variables will be listed by subject. Summary statistics will be provided.

Relevant medical history, current medical conditions, results of laboratory screens, drug tests and any other relevant information will be listed and summarized.

11.3 Treatments (study drug, rescue medication, other concomitant therapies, compliance)

Data for study drug administration, and concomitant therapies will be listed and summarized.

11.4 Analysis of the primary variable(s)

The primary objective of this study is to assess the effect of LFG316 on the reduction of intravascular hemolysis in PNH patients as assessed by reduction in serum LDH levels after the first 4 weeks of treatment and during the entire treatment period.

11.4.1 Variable(s)

The primary efficacy variable for assessing the effect of LFG316 over the first 4 weeks of treatment is response rate where a patient will be considered a responder if the percentage reduction from baseline in serum LDH is at least 60% at any time up to and including week 4 for that patient.

The primary efficacy variable for assessing the effect of LFG316 over the entire treatment period is the actual serum LDH value measured at multiple time points during the study.

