3.1 Study design

This is an open-label, non-controlled study in patients with PNH. Approximately 10 patients will be enrolled in the study. At the time that Protocol amendment v07 is effective, no additional patients will be enrolled. The study drug will be administered via i.v. infusion at the dose level of 20 mg/kg every 14 days. Patients participating in study will have an option to either complete period 3 Follow up and Study Completion evaluation or continue in study period 4 that is pre-requisite to join the long-term extension study CLNP023C12001B, that is separate to this study protocol. Patients who are potentially eligible and willing to participate in the LNP023 long-term extension study will join period 4, where treatment will be converted from LFG316 to LNP023 200 mg b.i.d.

The study will consist of a 60-day screening period to assess eligibility and conduct vaccinations if required (for all patients not previously vaccinated at least 2 weeks prior to first dosing or if prior vaccination cannot be confirmed). An extensive screening window (up to 60 days) is planned in order to comply with local vaccination requirements, if available and deemed necessary at the investigator's discretion. Safety evaluation assessments requiring blood and urine samplings, pregnancy test, pulmonary function test, ECG, patient reported outcomes, and assessment of number of blood transfusions should be performed no longer than 4 weeks prior

to the planned dosing day. Subjects who meet the eligibility criteria at screening will be admitted to baseline (Day 1) evaluations. The patients will enter treatment period 1, and will receive infusions of LFG316 every 14 days, days 1, 15 and 29 (3 administrations).

At the end of period 1, efficacy on hemolytic activity by serum LDH will be assessed. All patients will then be allowed to enter the optional treatment period 2, and will receive infusions of LFG316 every 14 days, and undergo the efficacy, PK, CCI and safety assessments for additional 48 weeks.

Following the 48-week treatment period 2, LFG316-responsive patients (assessed based on investigator's judgment) will be allowed to enter an additional third extension period of up to 260 weeks (extension period 3).

The LFG316 treatment for all patients will be completed by end of 2021 regardless of each individual treatment period.

[figure not shown]

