The study is divided into 4 parts: treatment period 1 (29 days), during which a total of approximately 350 mL of blood will be collected, treatment period 2 (335 days), during which approximately 700 mL blood will be collected, treatment period 3 (up to 5 years duration), during which the maximum collected blood volume will be approximately 1300 mL, and period 4 (approximately 5 months) when approximately 220 mL of blood will be collected. The maximum blood volume over any 12 week period will not exceed 450 mL. Additional samples for monitoring of any safety findings would be in addition to this. This is not considered to be a risk for this population.

Women of child bearing potential should be informed that taking the study drug may involve unknown risks to the fetus if pregnancy were to occur during the study and agree that in order to participate in the study they must adhere to the contraception requirement for the duration of the study. If there is any question that the subject will not reliably comply, they should not be entered in the study.

There may be unknown risks of LFG316 which may be serious and unforeseen.

In the absence of any additional anticipated or known risks of complement inhibition in relationship with COVID-19, the benefit/risk ratio of this study protocol and of both investigational drugs in particular, LFG316 and LNP023, remains unchanged during the COVID-19 pandemic.

3.6.1 Risks and benefits for period 4

The risks associated with the use of LNP023 are those inferred by its mechanism of action as well as the findings of preclinical safety studies. The most relevant risks and mitigation strategies are described below and a more comprehensive description of safety findings to date is available in [Section 1.1.1.3.2](#) and in the IB.

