11.4.2 Statistical model, hypothesis, and method of analysis

Proof of concept will be based on LDH levels during the first four weeks. A positive sign of efficacy is when:

- The estimated median response rate is at least 50%

Commercially Confidential Information

For the analysis of serum LDH values from multiple time points, a longitudinal model analysis of log-transformed LDH levels over time pre- and post-treatment will also be performed.

Longitudinal modelling will include individual and treatment average graphical presentations over time incorporating any historical LDH data collected so as to better put post-treatment changes in context.

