11.4.4 Supportive analyses

For comparison with the Bayesian analysis above, supportive analyses are in the frequentist paradigm giving the possibility of incorporating meaningful prognostic characteristics, such as being carriers or not of the minor allelic variant of C5, in modelling the response rate as binary data in logit models.

Alternative longitudinal model analyses of log-transformed LDH levels over time pre- and post-treatment may also be performed, to assess the sensitivity of the primary analysis to missing data, any deviations from assumptions, and to also assess the impact of prognostic factors on conclusions.

Commercially Confidential Information

Additionally serum LDH at each timepoint will also be summarized in terms of the number and percentage of patients achieving a reduction in LDH to within the normal limits.

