7.1 Primary objective

7.1.1 Variables

The primary efficacy variable is response rate where a patient will be considered a responder if the percentage reduction from baseline in serum LDH is at least 60% at any time up to and including week 4 for that patient.

The primary efficacy variable for assessing the effect of LFG316 over the entire treatment period is the actual serum LDH value measured at multiple time points during the study.

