7.1.6 Supportive analyses

Commercially Confidential Information

Longitudinal analysis will firstly include individual and average graphical presentations over time incorporating any historical LDH data collected so as to better put post-treatment changes in context. If deemed potentially useful, longitudinal statistical modelling will be used to look at changes within subjects as well as across subjects.

Additionally serum LDH at each timepoint will also be summarized in terms of the number and percentage of patients achieving a reduction in LDH to within the normal limits.

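### Does counting any single LDH fall of at least 60% up to week 4, with no visible Day 29 response rate, undermine the proof-of-concept conclusion?

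*Protocol*

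**What the plan says.** Protocol 11.4.1 defines the week 4 primary variable: "a patient will be considered a responder if the percentage reduction from baseline in serum LDH is at least 60% at any time"; the window closes at week 4. SAP 7.1.1 repeats the rule ("is at least 60% at any time up to and including week 4 for that patient"), as does the synopsis. No confirmation is required. The endpoint in Protocol 2.1 is likewise a reduction within the first 4 weeks. The visible proof-of-concept criterion in Protocol 11.4.2 is "The estimated median response rate is at least 50" per cent.

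Two other sentences refer to the end of the window. Protocol 3.1 says "At the end of period 1, efficacy on hemolytic activity by serum LDH will be assessed", and the opening of Protocol 11.4 speaks of "reduction in serum LDH levels after the first 4 weeks of treatment". Period 1 lasts 29 days (Protocol 3.6), and Table 8-1 schedules chemistry including LDH on Days 8, 15, 22 and 29.

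Beyond the response rate, both documents name a second primary variable: the actual LDH value at multiple time points over the entire treatment period. Protocol 11.4.2 commits to a longitudinal analysis of log LDH with individual and average plots. Protocol 11.4.4 and SAP 7.1.6 add, at each time point, "the number and percentage of patients achieving a reduction in LDH to within the normal limits". Laboratory values are listed by patient and visit and summarised by visit (Protocol 11.5.2, SAP 8.1.2).

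**The concern.** Taking the best of four noisy values can only raise the response rate compared with a single fixed visit, because Day 29 is itself one of the four. A patient who dips on Day 8 and rebounds by Day 29 still counts in full. Since the protocol elsewhere speaks of assessing efficacy at the end of period 1, a reader may expect a rate at that visit.

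The planned per-visit count does not supply it. It uses the normal limit, which coincides with a 60% fall only at a baseline of 1/0.4 = 2.5 times the upper limit of normal, while entry requires only 1.5 times. The SAP also makes modelling optional: "If deemed potentially useful, longitudinal statistical modelling will be used". What would be at stake is a positive proof of concept resting on transient dips or measurement noise.

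**Working it through.** **1. Consistency.** The synopsis, Protocol 11.4.1 and SAP 7.1.1 state the same rule. It fits the endpoint in Protocol 2.1, which is a fall within, not at the end of, the first 4 weeks. The sentence in Protocol 3.1 reads naturally as the moment when the period 1 data are evaluated. The one in 11.4 loosely restates the objective. Neither defines a Day 29 endpoint.

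**2. How much the any-time rule could matter.** The plan shows no figure to reproduce, because the sample-size text is redacted.

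Inputs from the documents:
- Qualifying ratio to baseline: at most 1 − 0.60 = 0.40.
- Four post-baseline draws (Table 8-1).
- Baseline is the average of pre-dose values (SAP 7.1.2).
- About 10 patients (Protocol 3.1).

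Assumptions, not in the documents:
- Two pre-dose draws (screening and Day 1).
- Independent log-normal within-patient noise, log-SD σ from 0.1 to 0.3.
- Between-patient log-SD τ of 0 or 0.3.
- The criterion read as at least 5 of 10, which symmetric beta priors give; the actual prior is redacted.

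Model: draw j has ratio r_j·exp(τb + σe_j)/B, where B is the mean of two exp(σe) terms and b and all e are standard normal. The any-time rate is P(at least one of four ratios ≤ 0.40); the Day 29 rate is P(fourth ratio ≤ 0.40). Then P(≥5/10) = Σ_{k=5..10} C(10,k) p^k (1−p)^(10−k). Each setting used 1,000,000 simulated patients.

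| True course | Any-time patient rate | Day 29 patient rate | P(≥5/10), any-time | P(≥5/10), Day 29 |
|---|---|---|---|---|
| No change, τ 0 or 0.3 | 0–8.5% | 0–3.0% | at most 0.08% | below 0.001% |
| 50% fall, constant, τ 0 | 12–64% | 4–29% | 0.4–89% | 0–14% |
| 50% fall, gradual, τ 0 | 5–48% | 4–29% | 0–58% | 0–14% |
| 60% fall, constant, τ 0 | 86–87% | 51–52% | above 99% | 64–68% |
| 60% fall, gradual, τ 0.3 | 52–65% | 50–52% | 68–90% | 63–67% |
| 70% fall, constant, τ 0 or 0.3 | 89–100% | 74–99% | above 99% | at least 97% |
| 80% fall, constant, τ 0 or 0.3 | 99–100% | 93–100% | about 100% | about 100% |

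Gradual courses use ratios 0.75, 0.60, 0.53, 0.50 (to 50%) and 0.70, 0.55, 0.45, 0.40 (to 60%).

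Worst no-effect case (σ = τ = 0.3, p = 0.085): the leading term is 252 × 0.085^5 × 0.915^5 = 0.00072, and all six terms sum to 0.00078, or 0.08%. With τ = 0 the largest value is about 4 in a million.

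The any-time rule therefore does not turn an inactive drug into a positive one, and for a large effect it changes nothing that matters. It makes a difference for true falls around 50% to 60%. A true 50% fall is a real drug effect, so a positive sign there is not a false positive in the usual sense.

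**3. Whether persistence is hidden.** It is not. LDH over the entire treatment period is a primary variable, and the protocol's longitudinal analysis is unconditional. With about 10 patients and four draws each, the by-patient listing has about 40 period 1 values after baseline, from which the Day 29 count can be made by hand.

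**4. Whether the summary is absent.** This cannot be known. Text is redacted in Protocol 11.4.2 and 11.4.4 and in SAP 7.1.2, 7.1.3, 7.1.4 and 7.1.6. SAP 1.1 places the table and listing shells in Module 7, and SAP section 5 refers to the output shell; that module is not among the public documents.

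**The case for a change.** The best opposing argument comes from the protocol itself. Section 3.3.1 anticipates breakthrough hemolysis towards the end of a dosing interval, as seen in LDH. Doses fall on Days 1, 15 and 29, so Days 8 and 22 are mid-interval, and Day 29, if drawn before the infusion, is end-of-interval. A response seen only mid-interval would count in full.

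Part of this stands. Near the threshold the two rates differ: by up to 35 points with a constant true 60% fall, full effect by Day 8, no between-patient spread and independent noise; by as little as 2 points with gradual onset and between-patient spread. It is also true that the normal-limits count is no substitute, and that the SAP's conditional modelling is weaker than the protocol's commitment. That last difference concerns the second primary variable, not the responder rule.

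It falls short of a defect for two reasons. A Day 29 rate would not isolate rebound: with a constant 60% fall, 34–35% of patients respond at some draw yet miss on Day 29 through noise alone. The individual profile is what tells a rebound from noise, and profiles are already planned as plots and listings. In addition, asking for that rate would leave both the primary definition and the proof-of-concept rule unchanged, so it is a wish for one more output.

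**Conclusion.** The concern does not hold. The any-time rule is stated consistently, agrees with the endpoint, and is a defensible choice for a small proof-of-concept study asking whether the drug can lower LDH substantially within 4 weeks. Its leniency is confined to true falls near the threshold: 2 to 35 percentage points at a true 60% fall. With no effect the chance of at least 5 of 10 is at most 0.08%, and with a 70% or 80% fall it is at least 97% under either rule. Persistence is covered by the second primary variable, the longitudinal analysis and the by-visit listings.

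The simulated figures rest on assumed LDH variability, time course and a 5-of-10 reading of a partly redacted criterion; another choice would move them. The consistency of the definition and the availability of Day 29 values do not depend on those assumptions.

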11.4.2 Statistical model, hypothesis, and method of analysis

Proof of concept will be based on LDH levels during the first four weeks. A positive sign of efficacy is when:

- The estimated median response rate is at least 50%

Commercially Confidential Information

For the analysis of serum LDH values from multiple time points, a longitudinal model analysis of log-transformed LDH levels over time pre- and post-treatment will also be performed.

Longitudinal modelling will include individual and treatment average graphical presentations over time incorporating any historical LDH data collected so as to better put post-treatment changes in context.

11.4.3 Handling of missing values/censoring/discontinuations

The study aims to replace subjects enrolled before protocol amendment 5 who discontinue before the end of period 1 for reasons other than safety and the primary responder analysis will be based on period 1 completers only, in a per protocol fashion.

Further longitudinal model analyses performed to assess the effect of missing data on the conclusions drawn from the primary analysis will include, if available, data from any subjects who discontinued early. Lack of efficacy will not be considered a missing value. Even if treatment is discontinued, LDH values should still be assessed in the eight-week follow-up period.

11.4.4 Supportive analyses

For comparison with the Bayesian analysis above, supportive analyses are in the frequentist paradigm giving the possibility of incorporating meaningful prognostic characteristics, such as being carriers or not of the minor allelic variant of C5, in modelling the response rate as binary data in logit models.

Alternative longitudinal model analyses of log-transformed LDH levels over time pre- and post-treatment may also be performed, to assess the sensitivity of the primary analysis to missing data, any deviations from assumptions, and to also assess the impact of prognostic factors on conclusions.

Commercially Confidential Information

Additionally serum LDH at each timepoint will also be summarized in terms of the number and percentage of patients achieving a reduction in LDH to within the normal limits.

11.5 Analysis of secondary CCI variables

The analysis of the two secondary endpoints of standard safety monitoring with increased vigilance for infections and measurement of serum concentrations of LFG316 are covered in [Section 9.1](#) (adverse events) and [Section 8.5](#) (pharmacokinetics) respectively. There will be no adjustment for multiplicity over the three main analyses of efficacy (primary), safety and PK (both secondary).

Commercially Confidential Information

11.5.1 Efficacy / CCI

The analysis of the primary efficacy endpoint of reduction in LDH is described above in [Section 11.4.2](#) and [Section 11.4.4](#).

Commercially Confidential Information

11.5.2 Safety

Adverse events

All information obtained on adverse events will be displayed as summary and by subject as per the secondary objective.

The number and percentage of subjects with adverse events will be tabulated by body system and preferred term. A subject with multiple adverse events within a body system is only counted once towards the total of this body system.

As this study has four treatment periods an adverse event starting in period 1 and continuing into the next period is counted only in the period 1. A subject with multiple adverse events within a body system and treatment period is only counted once towards the total of this body system and treatment period. There will be three summaries of AEs, at the end of treatment period 1; periods 2 and 3 combined; and period 4.

Vital signs

All vital signs data will be listed by subject and visit/time and if ranges are available abnormalities (and relevant orthostatic changes) will be flagged. Summary statistics will be provided by visit/time.

ECG evaluations

All ECG data will be listed by subject and visit/time, and abnormalities will be flagged. Summary statistics will be provided by visit/time.

Clinical laboratory evaluations

All laboratory data will be listed by subject and visit/time and if normal ranges are available abnormalities will be flagged. Summary statistics will be provided by visit/time.

11.5.3 Pharmacokinetics

Total LFG316 concentration data will be listed by subject, and visit/sampling time point. Descriptive summary statistics will be provided by visit/sampling time point, CCI

Summary statistics will include mean (arithmetic and geometric), SD, CV (arithmetic and geometric), median, minimum and maximum. An exception to this is Tmax where median, minimum and maximum will be presented. Commercially Confidential Information

Pharmacokinetic parameters will be calculated as described in [Section 8.5](#) and will be listed by subject.

Commercially Confidential Information

11.5.5 Other assessments

Commercially Confidential Information

